7.2.2.4.3. Supportive care guidelines

All required supportive care should be delivered according to local practice.

7.2.2.4.4. Radiotherapy Quality Assurance

A radiotherapy quality assurance (RTQA) program will be instigated to ensure the safety and consistency of radiotherapy delivery at participating sites. For further information please see Appendix 5.

7.2.3 Annual follow-up

Patients should have annual follow-up mammography carried out until 5 years post-randomisation. Where local protocol dictates that patients are not reviewed in clinic on an annual basis, arrangements should be made to contact the patient by telephone following the outcome of surveillance mammography. Any planned additional follow-up for patients in the surgery arm of the trial will be in accordance with local guidelines.

7.2.3.1 Mammography

Patients must be invited to attend for annual mammography for 5 years following randomisation. Beyond 5 years follow-up will be in accordance with local guidelines. In the majority of cases it is anticipated that this will be in the NHSBSP.

Following annual mammography, patients should be informed of the outcome of their mammogram as soon as possible and ideally within two weeks of the mammogram being carried out.

If a patient fails to attend for a mammogram appointment, a second appointment should be sent. If the patient fails to attend the second appointment, the patient's GP should be contacted to ensure that the patients address is correct. If the address is correct, a letter should be sent to the patient and their GP by the site research team, asking them to contact their research nurse. If a patient does not respond to this invitation, the patient should be contacted by telephone. The site research team must make every effort to ensure that patient contact details are up to date.

7.2.3.2 Ipsilateral mammographic indications for patient recall

Mammographic changes which would warrant recall for further investigation are:

- Developing asymmetry or mass around the marker clip at the VAE site
- A new non-calcified lesion in either breast which is not definitively benign
- A new cluster of microcalcification in either breast which is not definitively benign

7.2.4 Relapse

All relapses will be treated as per local practice. As soon as definite confirmation has been obtained that a patient has relapsed or has developed a new second primary cancer, the applicable form should be completed and submitted to the SMALL Trial Office; Ipsilateral Breast Disease (please also forward a copy of the patient's anonymised pathology report to the SMALL Trial Office), Contralateral Breast Disease or Distant Metastases Form. See Table 1 for definitions of relapse.

Patients who relapse or develop a new second primary cancer should remain on follow-up.

Table 1: Definition of Relapse

Type of Relapse	Definition
Loco-regional relapse (invasive or in situ)	A loco-regional relapse is defined as a recurrence of breast cancer (either invasive or in situ) in the ipsilateral breast/chest wall, axillary lymph nodes and/or ipsilateral supraclavicular fossa and/or internal mammary nodes
Distant relapse	Distant recurrence is defined as a recurrence (metastasis) of breast cancer developing beyond the ipsilateral breast/chest wall, axillary lymph nodes and/or ipsilateral supraclavicular fossa and internal mammary lymph nodes
New primary	Confirmation of the presence of a second unrelated and new cancer. For the purposes of SMALL this will include contralateral malignant breast disease (either invasive or in situ)

7.2.5 Related Adverse Event Review

Protocol-related AEs will be collected post trial treatment, at 6-months post randomisation and annually from randomisation on the CRF from years 1-5, with reference to the defined Surgical Complications and Definitions (see Appendix 4). Serious Adverse Events (SAEs) will be reported from study entry until 5 years post-randomisation in accordance with Section 12 Adverse Event Reporting.

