7.1.6 Related adverse event review

Protocol-related adverse events (AEs) will be collected post trial treatment, at 6-months post randomisation and annually from randomisation on the CRF from years 1-5, with reference to the defined Surgical Complications and Definitions (see Appendix 4) for events occurring within 30 days of trial treatment or CTCAE thereafter. Serious Adverse Events (SAEs) will be reported from trial entry until 5 years post-randomisation in accordance with Section 12 Adverse Event Reporting.

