12.2 Reporting Procedure

12.2.1 Site

12.2.1.1 Adverse Events

Protocol-related AEs should be recorded in the AE section of the Treatment Form and Annual Followup Form with reference to the defined Surgical Complications and Definitions (see Appendix 4).

SAEs will be reviewed using the Common Terminology Criteria for Adverse Events (CTCAE), version 4.0 (see Appendix 3). Any SAEs experienced by the patient but not included in the CTCAE should be graded by an Investigator and recorded on the AE Form using a scale of (1) mild, (2) moderate or (3) severe. For each sign/symptom, the highest grade observed since the last visit should be recorded.

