APPENDIX 3 – COMMON TOXICITY CRITERIA GRADINGS

Toxicities which are reportable as a Serious Adverse Event will be recorded according to the Common Terminology Criteria for Adverse Events (CTCAE), version 4.0. The full CTCAE document is available on the National Cancer Institute (NCI) website, the following web address was correct at the time that the protocol was approved:

http://ctep.cancer.gov/protocolDevelopment/electronic_applications/ctc.htm

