APPENDIX 4 – SURGICAL COMPLICATIONS & DEFINITIONS

Post-operative complications occurring within 30 days;

- 1. Seroma (breast/axilla) a collection of serosanginous fluid in the wound
 - a. Requiring aspiration 1-2 times
 - b. Requiring aspiration 3 or more times
- 2. Haematoma (breast/axilla) a collection of blood in the wound
 - a. Minor (conservative management)
 - b. Major 1 requiring evacuation in clinic +/- US guidance (no GA)
 - c. Major 2 requiring surgical evacuation (GA)
- 3. Wound infection (breast/axilla)
 - a. Minor (oral antibiotics)(breast/axilla)
 - b. Major 1 (iv antibiotics)(breast/axilla)
 - c. Major 2 (surgical drainage +/- debridement)(breast/axilla)
- 4. Delayed wound healing/skin flap necrosis
 - a. Minor (conservative management)
 - b. Major 1 requiring surgical debridement in clinic (no GA)
 - c. Major 2 requiring surgical debridement in theatre (GA)
- 5. Nipple necrosis
 - a. Minor (conservative management)
 - b. Major 1 (requiring debridement)
 - c. Major 2 (complete NAC loss)
- 6. Wound dehiscence (breast/axilla)
 - a. Minor (conservative management)(breast/axilla)
 - b. Major (requiring return to theatre)(breast/axilla)
- 7. In-hospital complication (including systemic complications
 - a. DVT/PE/MI/LRTI/UTI/transfusion/unplanned HDU/ITU admission
- 8. Readmission to hospital within 30 days
 - a. No
 - b. Yes, for complication listed above (1-7)
 - c. Yes, for other reason

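### Sections 7.1.6, 7.2.5 and 12.2.1.1 give conflicting rules for grading non-serious related adverse events after 30 days, and the VAE arm has no applicable scale

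*Protocol*

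**What the plan says.** **Surgery arm (7.1.6).** Related events are collected after treatment, at 6 months and yearly in years 1 to 5. They are referred to Appendix 4 "for events occurring within 30 days of trial treatment or CTCAE thereafter". No CTCAE version is given here.

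**VAE arm (7.2.5).** The schedule is the same: "Protocol-related AEs will be collected post trial treatment, at 6-months post randomisation and annually from randomisation on the CRF from years 1-5". The reference standard is Appendix 4 alone: "with reference to the defined Surgical Complications and Definitions (see Appendix 4"). There is no 30-day limit and no CTCAE clause.

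**General rule (12.2.1.1).** This section makes no distinction by arm. "Protocol-related AEs should be recorded in the AE section of the Treatment Form and Annual Followup Form", again with reference to Appendix 4. CTCAE is brought in for serious events: "SAEs will be reviewed using the Common Terminology Criteria for Adverse Events (CTCAE), version 4.0".

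**Appendix 3.** It describes CTCAE in terms of serious events: "Toxicities which are reportable as a Serious Adverse Event will be recorded according to the Common Terminology Criteria for Adverse Events (CTCAE").

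**Appendix 4.** It is headed "Post-operative complications occurring within 30 days". Its items are seroma, haematoma, wound infection, delayed healing or flap necrosis, nipple necrosis, dehiscence, in-hospital complications and readmission within 30 days.

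**The concern.** Appendix 4 is a list of early post-operative complications. It has no entry for lymphoedema, numbness, paraesthesia or chronic pain. Section 7.2.5 nevertheless makes it the only reference standard for VAE visits that run to year 5, while 7.1.6 moves the surgery arm to CTCAE after day 30. Taken at their word, the two sections give the same late effect a severity grade in one arm and no applicable scale in the other. Sites and patients both know the allocation, so nothing masks this difference in recording.

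Late morbidity matters to the argument for VAE. Section 1.1 names lymphoedema, numbness and paraesthesia as the cost of sentinel node biopsy. Section 1.2.1 gives the avoidance of long-term surgical complications as a possible gain. The trial collects late effects on purpose, and 16.5 sends all adverse events to the data monitoring committee. If late events are graded by different rules, a table that sets the arms side by side may reflect the recording rule as well as the treatments. Grades not captured at the visit are hard to reconstruct later.

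**Working it through.** No calculation decides this point, and the protocol has no figure to reproduce. The check is a comparison of the rules.

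| Source | Arm | Non-serious, up to 30 days | Non-serious, after 30 days | Serious |
|---|---|---|---|---|
| 7.1.6 | Surgery | Appendix 4 | CTCAE, version not given | refers to Section 12 |
| 7.2.5 | VAE | Appendix 4 | Appendix 4 only (a 30-day list) | refers to Section 12 |
| 12.2.1.1 | Both | Appendix 4 | Appendix 4 only (a 30-day list) | CTCAE v4.0 |
| Appendix 3 | Both | – | – | CTCAE v4.0 |

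1. **Up to 30 days** all three sections agree on Appendix 4. The complications outcome in 16.2.2 is confined to this window, with one definition for both arms. Under 16.3 it is reported descriptively without a test. It is therefore unaffected.
2. **Serious events** use CTCAE v4.0 in both arms and are unaffected.
3. **Non-serious events after 30 days** are where the rules part:
   - If sites follow 7.1.6 and 7.2.5, surgery events are graded by CTCAE and VAE events have no applicable scale.
   - If sites follow 12.2.1.1, the arms are treated alike, but late events have no applicable scale in either arm and the CTCAE clause in 7.1.6 is overridden.
   - If practice is mixed, grading varies by site as well as by arm.
4. **Does Section 12 repair 7.2.5?** No. It supplies no late grading rule for non-serious VAE events, and it also contradicts 7.1.6.
5. **Are late VAE events still captured?** Yes. The Annual Follow-up form in 13.1 has a field for lasting protocol-related effects, with no distinction by arm, and 12.1.3 sets one reporting period to 5 years. What is missing is the grading scale, not the place to record the event.

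**Number of women covered by the wording.** Section 16.7 plans 533 VAE and 267 surgery patients and assumes 20% re-excision in each arm. In the VAE arm, 0.20 × 533 = 106.6, or about 107 women, would go on to surgical excision. Under 7.2.2.1, those who do so because excision is incomplete on imaging also have sentinel node biopsy. They would meet the same kind of axillary procedure as the surgery arm, yet 7.2.5 names no late scale for them. These are headcounts, not an estimate of bias.

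**The case against.** The strongest reply is that this is a drafting mismatch with little consequence. Section 12.2.1.1 gives a single rule for both arms, so the protocol can be read without any difference between arms, and the odd clause is then the one in 7.1.6. Late events are collected at the same visits and on the same form in both arms. Late arm and breast symptoms are also measured symmetrically by the QLQ-BR23 at baseline and at 6, 12, 36 and 60 months, and 16.3 compares quality of life between arms.

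Much of this stands. The difference does look like an omission rather than a design choice, and the symmetric collection limits the harm. It does not remove the conflict. Staff who treat a patient will read the section for her arm, and reading 12.2.1.1 as the governing rule leaves late non-serious events without a suitable scale in both arms. The QLQ-BR23 covers only women who consent to the quality of life sub-study, and it is not an adverse event grade.

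A reader might go further and infer that the late-morbidity comparison is biased towards VAE. The documents do not support that. No late-morbidity outcome or comparison is defined; lymphoedema and similar effects appear in the rationale but not among the outcome measures in 2.2.2. Nor is the direction settled. An ungraded VAE event might be left out of a table, which would flatter VAE, or counted whatever its severity, which would not. It would also be too strong to say that late VAE events cannot be recorded.

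**Conclusion.** The contradiction is real and should be corrected. Three sections disagree on how non-serious related events after 30 days are graded, and on the arm-specific text the VAE arm has no applicable scale. What is at risk is the comparability between arms of descriptive late adverse event tables and of the safety data sent to the data monitoring committee. No defined outcome is affected.

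The size and direction of any bias are unknown, because the protocol gives no late event rate. The loss of comparability rests on one assumption, that sites follow the section written for the patient's arm. If they follow 12.2.1.1 instead, the arms are alike but late events are poorly graded in both. The importance is minor to moderate; the case for acting is that the correction costs very little and the lost grades are hard to recover.

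**What to change.** Put one identical clause in 7.1.6, 7.2.5 and 12.2.1.1, built on the existing 7.1.6 wording and applied to both arms: Appendix 4 for events within 30 days of trial treatment, CTCAE v4.0 thereafter. Three details go with it:

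- State the version in 7.1.6, and extend Appendix 3 so that it is not read as confining CTCAE to serious events.
- Keep the 30-day window consistent with 16.2.2, which counts from the protocol-defined surgery or VAE. Broader wording, such as any trial procedure, could restart the window after a second operation and depart from the outcome definition.
- Give the late-effects field on the Annual Follow-up form a CTCAE term and grade for both arms.

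The cost is a clause in three sections, a line in Appendix 3, one form field and a note to sites. It changes how data are recorded, not how patients are managed, and it leaves the sample size and the defined outcomes as they are.

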7.2.6 Survival

Sites should report patient deaths by completing the Death Form immediately upon being made aware of the event. Every effort should be made to obtain a date and cause of death.

7.3 Protocol Deviations and Patient Withdrawal

7.3.1 Protocol deviations

The details of the protocol deviation (date, reason and type of deviation) should be clearly documented in the source data. A Deviation Form should be completed to notify the SMALL Trial Office of the deviation.

Patients will continue to be followed-up on an intent-to-treat basis.

7.3.2 Withdrawal of consent

Patients may withdraw consent at any time during the trial. For the purposes of this trial, three different types of withdrawal are defined:

- The patient would like to withdraw from the randomised allocation, but is willing to be followed up according with the Schedule of Assessments (i.e. the patient has agreed that data can be collected and used in the trial analysis)
- The patient would like to withdraw from the randomised allocation and does not wish to undergo study assessments in accordance with the Schedule of Events but is willing to be followed up at standard clinic visits (i.e. the patient has agreed that data can be collected at standard clinic visits and used in the trial analysis)
- The patient would like to withdraw from the randomised allocation and is not willing to be followed-up for the purposes of the trial at any further visits (i.e. only data collected prior to the withdrawal of consent can be used in the trial analysis)

The details of withdrawal (date, reason and type of withdrawal) should be clearly documented in the source data. A Withdrawal of Consent Form should be completed to notify the SMALL Trial Office of the patient's withdrawal.

7.4 Concurrent Studies

Investigators wishing to enrol patients into another trial should contact the SMALL Trial Office in the first instance. The SMALL Trial Management Group (TMG) will consider the enrolment of SMALL patients into other trials that do not interfere with the analysis of the primary outcome or introduce bias. Examples may include trials of imaging or supportive treatment. The SMALL Trial Office will maintain a contemporary record of trials approved by the TMG. Where a trial has not been considered, the SMALL Trial Chief Investigator will provide advice based on the above principles.

8. QUALITY OF LIFE

8.1 Quality of life

The primary QoL aspect of the trial examines the hypothesis that the psychological well-being of women undergoing minimally-invasive VAE of small screen-detected breast cancers is not adversely affected by this approach, when compared standard surgical treatment. In addition, these QoL outcomes will inform future women diagnosed with small, good prognosis invasive breast cancer through the NHSBSP. Patients will be asked to complete questionnaires at different time-points, which will assess quality of life outcomes including psychological adjustment, anxiety and depression, body image and satisfaction with breasts, These will be completed at the time points summarised in Table 2.

8.1.1 EORTC QLQ-C30 and BR 23

The EORTC QLQ-C30 is a validated instrument for evaluating quality of life in patients participating in clinical trials. The core module incorporates nine multi-item scales (functional, symptomatic and a global health and quality of life scale)³⁴. The breast- specific module (QLQ BR23) was designed to be used in conjunction with the QLQ-C30 and consists of 23 items covering symptoms and side-effects related to different treatment modalities (including both the breast and arm), as well as body image, sexuality and future perspectives³⁵.

8.1.2 EuroQoL EQ-5D

The EQ-5D is a health status measure comprised of 5 attributes or dimensions - mobility, self-care, usual activity, pain/discomfort and anxiety/depression³⁶. The single summary scores derived from the EQ-5D can be used in QALY analysis and in cost- effectiveness and cost-utility analysis.

8.1.3 BREAST-Q (breast conserving therapy module)

The BREAST-Q is a patient-reported outcome instrument designed to evaluate outcomes among women undergoing different types of breast surgery and includes a BCT (breast conserving therapy) module appropriate to the patient population in this study³⁷. The BREAST-Q comprises two over-arching themes, which are patient satisfaction and health-related quality of life. Body image is an important concept for many women undergoing treatment for breast cancer, and it is possible that there may be differences in body image perception and satisfaction with breasts between the conventional surgery arm and the VAE arm, which is the rationale for utilising the BREAST-Q in this study.

	Time points (months from randomisation)						
Questionnaires	Baseline	6	12	24	36	48	60
EORTC QLQ-C30 & BR23	~	~	~		~		~
BREAST-Q	~		~	~	~	~	~
Euro-QoL EQ-5D	~	~	~	~	~	~	~

Table 2: Timeline for Quality of Life Questionnaires

With the exception of the baseline QoL questionnaires, which will be completed by the patient prior to randomisation, all other questionnaires will be distributed directly to the patients' home address by the SMALL Trial Office for completion at the designated time points.

Site research teams should inform the SMALL Trial Office immediately upon becoming aware of any changes to patient contact details by completing and returning the Change of Patient Contact Details Form.

9. HEALTH ECONOMICS

9.1 Form of the Health Economic Evaluation

If VAE is found to be an effective approach to help de-escalate the need for surgery in the treatment of small screen-detected breast cancer then it is likely that there will be important cost implications for the health care sector. For example, the patient will avoid initial standard surgery but will still receive adjuvant radiotherapy or endocrine treatment (according to local protocol) and will undergo mammographic surveillance, so the impact on resources and quality of life may or may not compare favourably to current standard treatment. If inpatient stay and resources associated with more invasive treatment are deemed unnecessary, then overall, resources may be saved. However, VAE may or may not incur unexpected or unscheduled costs due to additional appointments for reassurance using health care resources (for example, in providing counselling). Therefore, all associated resource use costs incurred by both approaches need to be assessed in conjunction with measures of effectiveness.

The aim of the economic evaluation is to determine the cost-effectiveness of VAE compared with standard surgery for small screen- detected breast cancer. The most appropriate type of analysis is a cost-effectiveness analysis which will be determined in two ways: a cost-effectiveness analysis will be undertaken based on a number of outcomes including the cost re-excision rate avoided at 10 years and cost per local recurrence of breast cancer avoided utilising the clinical outcome data collected within the trial. In addition, a cost-utility analysis will be undertaken to calculate the cost per additional quality-adjusted life year (QALY) gained. The utility values required to calculate QALYs will be obtained by administering the EuroQol EQ-5D questionnaire at the time points described in the PRO section. In the first instance, the evaluation will consider costs incurred by the health service in the delivery of both treatment pathways. However, information on costs incurred by patients will also be collected in order that an evaluation from a wider societal perspective can also be undertaken.

9.2 Cost Data Collection

Data collection will be undertaken prospectively for all trial patients so that a stochastic cost analysis can be undertaken. The process of collecting resource use data will be undertaken separately from data collection on unit costs.

The main resource uses to be monitored from the trial by trial staff (but not directly from the patients) include the following:

- Consultation time required to explain each procedure for explanation and consent (captured in a staff questionnaire or trial data collection sheet)
- VAE and surgical procedures (identification of procedures will be collected as part of the trial data collection; resource use associated with alternative procedures will be collected from time and motion study where appropriate or staff/expert opinion)
- Adjuvant therapy (which is provided according to local protocols and will differ across centres; this will be captured by a survey of protocols from the range of centres and the full range will be tested in the probabilistic sensitivity analysis)
- Resource use involved with mammography procedures (from a staff survey questionnaire and/or HRG cost data for mammography)
- Costs involved with other related procedures, including level of health care professional involvement in the procedure, equipment required, overheads, consumables and drugs including anaesthesia (procedures used will be identified from staff and trial data collection sheet; resource use will be collected from health care professionals in the various centres via time and motion study or expert opinion as appropriate)
- Any additional procedures required where initial treatment is unsuccessful or incomplete (Trial participating staff)
- Duration of inpatient stay for the surgical procedure (Trial data collection sheets)

Information on additional related primary or secondary care contacts will also be collected from women to ensure any resulting resource use from additional complications is recorded. The best approach to this data collection is likely to be the cross-sectional approach to investigate community-based healthcare and participant resource use for the first 5 years post randomisation, which follows that used by the ProtecT study. A patient resource use questionnaire is used to collect patient data, on private travel for hospital appointments and time off work, for example, with the aim of obtaining cross-sectional

community based healthcare and participant resource use for the first 5 years post randomisation. However, to achieve this, a specific resource use questionnaire is distributed to all women at one time point. This approach will capture some women at year one post-randomisation, some at 2 years etc. The approach can be used to ensure that no woman receives more than one questionnaire. The questionnaire will be issued at one time point and for the targeted women it will be at 4 months, 8 months and 12 months post-randomisation, depending on when they were randomised. In each case the requested information will relate to their resource use in the previous 4 months. In the 18-60 months questionnaires women can be asked about resource use in the previous 6 months. This approach would capture specific resource use for all women randomised into the study for complete coverage of five years, and follows the success of capturing the analogous data for men in the NIHR-HTA funded ProtecT and CAP studies currently in progress for prostate cancer. Unit costs will be obtained and attached to resource items in order that a cost can be calculated for each trial patient. Published sources for these costs will include Unit Costs of Health and Social Care and NHS Reference costs. Also, some primary cost data will be collected from a representative sample of participating hospitals. In addition, the setup costs of the trial will be estimated and additional analyses will be undertaken including these costs. In order to consider the wider cost implications of the interventions, a patient cost questionnaire will be administered to all trial patients at the suggested year 5 time-points. The questionnaire will contain questions to determine out of pocket expenses incurred (e.g. transport costs) when attending for treatment and private time costs including time lost from work.

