Currently, patients with screen-detected oestrogen receptor (ER) positive breast cancer undergo surgical excision (usually image-guided), under general anaesthesia, together with sentinel lymph node biopsy (SLNB) to establish whether there is any axillary lymph nodal disease. Surgery is generally breast conserving surgery, and is carried out on a day-case basis in the majority of patients, with axillary SLNB carried out at the same time. Following surgery, the tumour is evaluated by histopathology to determine complete excision, as denoted by the absence of tumour cells at the margin of the removed breast tissue (clear resection margins). However, in the UK, up to 20% of patients have histopathological involvement of the resection margins, necessitating a second procedure to ensure that these are cleared³. Similar rates of re-excision have been reported worldwide⁴. The need for re-excision is based on the finding that historically, in older breast cancer studies, positive margins have been associated with an increased risk of local recurrence of tumour within the breast. However, after much debate about what constitutes a "clear" margin, many international centres accept the pathological definition of "no tumour at the inked resection margin", and have demonstrated excellent long-term local recurrence rates⁵. Following successful breast conserving surgery, the vast majority of patients will receive adjuvant radiotherapy to the breast and systemic hormonal therapy⁶. However, breast conserving treatment may have significant associated complications, with early complication rates of up to 25% reported in a recent meta-analysis⁷. Furthermore, breast conserving surgery may have poor cosmetic outcomes⁸, which may adversely impact on patient satisfaction and quality of life^{9,10}.

With respect to the management of the axilla in this patient population, the incidence of axillary nodal disease is known to be low, and ultrasound +/- core biopsy/fine needle aspiration cytology of the axilla has been shown to have an extremely high negative predictive value in the NHSBSP³. Furthermore, even in the context of a positive SLN, excellent regional control can be achieved in the axilla without further surgical dissection¹¹, and information on the extent of nodal status does not usually influence treatment selection¹², nor indeed change long-term prognosis¹³. Data supporting the omission of axillary

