7.1.2.3 Radiotherapy

The use of post-surgical radiotherapy in the surgery arm of the trial should be in accordance with local MDT recommendation. Radiotherapy may be prescribed according to agreed local protocols. Data on radiotherapy use including regimen and fractionation will be collected on the CRF. As radiotherapy in the standard surgery arm of SMALL may be omitted, this arm of the study is compatible with the PRIMETIME study and therefore patients may be offered entry to PRIMETIME.

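### Section 9.2 takes adjuvant therapy for the costing from a survey of centre protocols, which cannot show what women in each arm received

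*Protocol*

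**What the plan says.** Section 9.2 opens with a patient-level aim: "Data collection will be undertaken prospectively for all trial patients so that a stochastic cost analysis can be undertaken". It later adds: "Unit costs will be obtained and attached to resource items in order that a cost can be calculated for each trial patient".

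The section then lists the main resource items with a source for each. For VAE and surgery, "identification of procedures will be collected as part of the trial data collection", and the resources used per procedure come from time-and-motion work or staff or expert opinion. For adjuvant therapy the entry reads "provided according to local protocols and will differ across centres; this will be captured by a survey of protocols from the range of centres". The spread between protocols is to be explored in the probabilistic sensitivity analysis. The entry mentions variation between centres. It does not mention arm, and it does not mention the CRF.

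Section 7 sets different rules by arm. After VAE, endocrine therapy (7.2.2.3) and radiotherapy (7.2.2.4) are both mandated, and 7.2.2.4.1 repeats that omitting radiotherapy is not appropriate. After surgery, endocrine therapy follows local guidelines (7.1.2.2) and radiotherapy follows the MDT. Section 7.1.2.3 adds: "As radiotherapy in the standard surgery arm of SMALL may be omitted, this arm of the study is compatible with the PRIMETIME study".

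The same section states: "Data on radiotherapy use including regimen and fractionation will be collected on the CRF". Section 7.2.2.4 says the same for the VAE arm. Endocrine use is captured in both arms, and section 13.1 lists a per-patient Adjuvant Treatment form.

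**The concern.** A survey of protocols shows what a centre normally does. It cannot show the MDT's decision for a particular woman, whether she entered PRIMETIME, or whether a woman in the VAE arm received her mandated course. Section 9.2 therefore names a source that cannot deliver the per-patient cost it promises.

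The gap matters because this item can differ systematically between arms. The stated aim of the evaluation is the cost-effectiveness of VAE against surgery, so a cost that falls more often on the VAE arm has to be attributed to that arm. If centre patterns are applied without regard to arm, VAE looks cheaper than it is.

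Section 9.1 points the same way. Its illustrative sentence says that the woman who avoids initial surgery "will still receive adjuvant radiotherapy or endocrine treatment (according to local protocol", whereas section 7 mandates both treatments for her. This is a minor wording point, but it suggests that section 9 was not aligned with the treatment rules.

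**Working it through.** The plan gives no figure to reproduce. The check compares the text first and then works out the possible size.

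**Text**

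| Item | VAE arm | Surgery arm | Source named in 9.2 |
|---|---|---|---|
| Radiotherapy | Mandated (7.2.2.4) | MDT decision, may be omitted (7.1.2.3) | Survey of centre protocols |
| Endocrine therapy | Mandated (7.2.2.3) | Local guidelines (7.1.2.2) | Survey of centre protocols |
| Initial procedure | VAE | Surgery | Trial data, plus time-and-motion work or opinion for content |

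For procedures, 9.2 separates who received the item from what it consumes. For adjuvant therapy it does not.

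**Inputs for size**

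- 533 VAE and 267 surgery patients (section 16.7).
- q, the share of surgery women who omit radiotherapy. The protocol does not give it. Section 1.1 says that after successful breast conserving surgery "the vast majority of patients will receive adjuvant radiotherapy to the breast and systemic hormonal therapy", so q is probably modest. Assumed: 5%, 10%, 15%.
- r, the share of VAE women who miss the mandated course. Not given. Taken as 0 first, then 2% as an illustration.

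**Step 1. True increment, full VAE receipt.** Courses per woman, VAE minus surgery: 1 − (1 − q) = q.

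**Step 2. One surveyed pattern p used in both arms.** The increment becomes p − p = 0, so the error is q: 0.05, 0.10 or 0.15 course per woman.

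**Step 3. Where the error falls.** This depends on what the survey returns.

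| q | Survey gives 1 − q: VAE courses not costed, 533 × q | Survey gives 1: surgery courses costed but not given, 267 × q |
|---|---|---|
| 5% | 26.65, about 27 | 13.35, about 13 |
| 10% | 53.3, about 53 | 26.7, about 27 |
| 15% | 79.95, about 80 | 40.05, about 40 |

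The two columns are alternatives. Each gives the same error of q per woman in the arm concerned, and hence in the increment.

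**Step 4. Some VAE women miss radiotherapy.** The true increment is (1 − r) − (1 − q) = q − r, and this is the error when one pattern is used. With q = 10% and r = 2% it is 0.10 − 0.02 = 0.08. If r exceeded q, the sign would reverse.

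**Step 5. Does the sensitivity analysis repair it?** The range to be tested runs across centres. If each draw of p is shared by both arms, the increment is p − p = 0 in every draw. If the arms are drawn separately from the same range, the increment averages 0. Neither is centred on q. The analysis would widen the uncertainty without moving the estimate.

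No money figure can be given, because the protocol contains no unit costs.

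**The case against.** The strongest reply is that nothing is lost. The CRF holds radiotherapy and endocrine data for each woman in both arms, and the annual follow-up form records other clinical trials, which could show PRIMETIME entry. An analyst could cost receipt by arm without changing trial conduct. On this view the general commitments to prospective per-patient costing govern the adjuvant entry, and the survey supplies only regimen content, which does vary by centre even where treatment is mandated. The mammography entry likewise names only a staff survey or reference costs. Detailed costing rules are also often left to a later analysis plan. Finally, the harm depends on a step the protocol does not state, namely using one pattern for both arms.

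Much of this stands. The data exist, the error is conditional, the course counts are scenarios and not forecasts, and the sentence in 9.1 is only illustrative.

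It does not remove the point. The entry says that adjuvant therapy is captured by the survey and does not limit the survey to content per course, whereas the procedures entry makes exactly that split. The general commitments conflict with the named source; they do not replace it. This is a stated method, not a detail left for later. That better data are already collected makes the named source harder to defend.

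**Conclusion.** The concern holds as a statement about section 9.2: the one source named for adjuvant therapy cannot show receipt by arm, although receipt differs by design. It does not mean that the trial fails to record adjuvant therapy.

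If one pattern is applied to both arms and VAE receipt is complete, the incremental cost of VAE is understated by q radiotherapy courses per woman. The values used for q and r are assumptions. If the survey is asked by arm, the error is smaller and its direction is not known. Endocrine therapy has a similar asymmetry, which is not quantified here.

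Only the health-economic evaluation is affected. Neither co-primary outcome is touched. The change is worth making because it removes a possible bias at almost no cost.

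**What to change.** - In section 9.2, take receipt, regimen and fractionation of radiotherapy, and use of endocrine therapy, from each woman's CRF (including the Adjuvant Treatment form), and cost them per patient by randomised arm.
- Keep the centre survey only for the resource content of each course.
- In the probabilistic sensitivity analysis, vary surgery-arm omission separately from VAE-arm receipt.
- In section 9.1, state that radiotherapy and endocrine therapy are both mandated after VAE.

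This takes about two sentences in section 9. It needs no new data collection and no change to trial conduct.
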